119 days. Bode and colleagues studied the safety and efficacy of Novolog insulin in 19
120 subjects used the same infusion set tubing for 7 days and overall, no negative effects
121 on glycemic control were observed during this period but it was noted that serum
122 glucose levels began to increase the longer the infusion set was used [17]. There have
123 been three published randomized trials assessing length of infusion set wear beyond 3
124 days. One study compared using insulin lispro to insulin aspart for 5 days of infusion set
125 wear [18]. There was no difference between the two insulins, with an average length of
126 infusion set wear of 98 and 96 hours, respectively. The researchers reported increased
127 glucose levels after 48 hours of wearing an infusion set and recommended changing
128 infusion sets every 2 days. We conducted a randomized, open-label, crossover study of
129 20 subjects who wore Teflon catheter (Quick-Set) and steel catheter (Sure-T) infusions
130 set for 38 weeks and 39 weeks respectively with no difference in the survival curves of
131 the infusion sets. The mean duration of wear was 5.5 days with a standard deviation of
132 1.9 days. Intersubject variation and the majority of failures were secondary to
133 uncorrectable hyperglycemia which indicates insulin flow occlusions [19]. Another
134 multicenter, crossover trial showed no difference in infusion set survival or mean
135 glucose in 20 type 1 diabetes subjects wearing the sets in either lipohypertrophied and
136 nonlipohypertrophied tissue [20].
137

138 **Etiology of Infusion Set Failures**

139 The underlying cause of intersubject variation in infusion set wear time is unknown but
140 in the prior infusion set studies time to failure was primarily associated with
141 hyperglycemia which did not improve with correction dose of insulin. In most of these
142 subjects, there was no overt back-pressure error from the pump. "Silent occlusions"
143 would be the most likely causative factor, and the additional slitted openings would
144 reduce the risk of silent occlusions and subsequent hyperglycemia (**Figure 2**). The
145 Lantern is designed to reduce failures due to kinking. Other less common causes for
146 set failure would probably not be affected by the Lantern; these include 10-15% being
147 pulled out by accident (tubing caught on a door handle for example), 6-12% from loss of
148 adhesiveness, 5-13% removed for pain and 5-10% for erythema/induration concerning

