184 insulin distribution in subcutaneous adipose tissue when using infusion set with Lantern
185 Technology. The infusion set was inserted into fresh human adipose tissue explants
186 with the aim to investigate the effect of catheter designs on the formation of
187 subcutaneous insulin depots. The study showed that the full functionality of the novel
188 insulin catheter is guaranteed independent of whether the catheter is open, kinked or
189 distally occluded. Therefore, it is not necessary to replace a kinked catheter or a
190 catheter with a clogged tip from the viewpoint of proper insulin delivery, which reduces
191 the incidence of unexplained hyperglycemia and even ketoacidosis which can be
192 associated with infusion set failures, as well as decreasing the discomfort for patients of
193 inserting multiple infusion catheters as a result of early failure. Study investigators
194 concluded that the new infusion catheter can provide a valuable contribution to patients'
195 well-being and safety.
196

197 In data that will be presented at the American Diabetes Association 2018 meeting,
198 glucose clamp studies were conducted in Graz among 16 patients with type 1 diabetes
199 (age 44.2 ± 15.4 years, BMI 24.5 ± 2.3 kg/m 2 , HbA1c 55 ± 8 mmol/mol, diabetes
200 duration 20 ± 9 years) with type 1 diabetes. All 16 patients wore the set for 7 days
201 without severe hypoglycemia or diabetic ketoacidosis. Geometric means of maximum
202 glucose infusion rates were comparable for days 1, 4 and 7. This preliminary data
203 strongly supports the safety of this infusion set and the need for real world testing of
204 longevity.
205

206 **Protocol Synopsis**

207 Part 1: Pilot Safety and Extended Wear Tolerability Study

208 This is a pilot study to obtain preliminary data upon which to base the length of wear for
209 the second part of the study. The study is not intended for registration purposes or to
210 support a 510(k) submission. The study will be conducted at one site: Stanford
211 University.
212

213 This study will enroll 24 subjects to establish the maximum length of Lantern infusion
214 set wear when 80% of sets are still functional (excluding accidental "pull-outs"). We will
215 plan for a staged enrollment, the first 10 subjects will be 18 or older. If there are no
216 untoward effects we will begin enrolling participants age 15-18. Each participant will
217 place the set and wear it for 10 days or until set failure and data will be collected on the

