218 cause of set failure. If a set is accidentally pulled out, it can be replaced by the subject.
219 Subjects will either complete a daily online questionnaire or they will be contacted daily
220 by research staff to determine if a set has failed, the cause of failure, and to record
221 measured erythema and edema at a failed infusion site. Failures are based on:
222

- 223 1. Presence of serum ketones with hyperglycemia
- 224 2. Unexplained hyperglycemia
3. Signs of infection at the infusion site

225 4. Pump occlusion alarm
226 5. Adhesive failure

227
228 Since infusion set failures will occur after variable lengths of wear, regularly scheduled
229 visits are unlikely to capture the day of an infusion set failure. Instead the subject will be
230 taught how to insert the set, measure erythema and induration with a ruler marked in
231 millimeters and to take a picture of the infusion site. Subjects will be instructed to text
232 the study team when they remove their infusion set and to send a picture of the infusion
233 site and measurements. If there is any evidence of an infection (≥ 10 mm of erythema or
234 induration), they will be asked to come in that day for an unscheduled visit.

[figure not shown]
235
236 Part 2: Extended Wear Randomized Controlled Crossover Study

237 This will be a masked, randomized controlled crossover study at Stanford University
238 (**Figure 4**). The study is intended for registration purposes and to support a 510(k)
239 submission. The planned duration of wear and visit schedule will be determined by the
240 results of Part 1. Participants, age 15 and over, will be randomized to wear the masked
241 investigational or control infusion set first. The control set is the Mio (used with
242 Medtronic pumps) or Inset II (used with other pump models) which are the precursors to
243 the Convatec Lantern and do not contain slits. Each participant will wear both the
244 investigational and control infusion set. Subjects will act as their own control.

245
246 At home subjects will examine their infusion site when they are changing an infusion set
247 and assess for signs of bleeding, local tissue reaction or infection. They will record
248 redness, induration, and bruising in mm, and call one of the investigators if there is
249 more than 10 mm of erythema or induration. They will be given a ruler for making these
250 measurements. If there is more than 3 mm of induration or redness they will be asked to

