743 Before beginning a larger cross-over study we would perform this pilot study to
744 determine the maximum length of Lantern infusion set wear when 80% are still
745 functional if failure was not due the infusion set being accidentally pulled out. This study
746 is not statistically powered.

747

748 **Part 2**

749 Primary Outcome

750 Our primary outcome will be time to failure of each infusion set. We have reviewed 353
751 weeks of infusion set wear from prior studies [19-20, unpublished data] and subjects
752 who wear the control set have an average length of wear of 5.1 days with a standard
753 deviation of 1.7 days and intra-subject correlation of 0.69. For a meaningful clinical
754 benefit, the subjects who wear the treatment set should extend wear by at least 1 day to
755 an average length of wear of 6.1 days. A sample size of 40 subjects will provide 95%
756 power to detect a difference of 1 day in the average length of wear in a two-sided test
757 with an alpha level of 0.05. A minimum of 25 subjects must be recruited for 80% power.

758

759 Exploratory Outcomes

760 Other outcomes will include – BMI, cause of infusion set failure, measurements of
761 erythema and induration, pump insulin delivery data, glucometer readings, ketone meter
762 data, average daily CGM blood glucose, DSAT/DDS score and infusion set
763 questionnaire.

764

765 We will summarize the other secondary measures using means, standard deviation,
766 medians, ranges, proportions and 95% confidence interval, as appropriate. We will also
767 explore the relationship between BMI, DSAT/DDS score and the time to failure primary
768 outcome. Finally, we will test if there is a significant change in the DSAT/DDS score
769 following participation in the clinical trial.

770 **CHAPTER 7: References**

1. The Diabetes Control and Complications Trial Research Group. "The effect of intensive treatment of diabetes on the development and progression of long-term complications in insulin-dependent diabetes mellitus. The Diabetes Control and Complications Trial Research Group." *N Engl J Med.* 1993 Sep 30;329(14):977-86.
2. Diabetes Control and Complications Trial/Epidemiology of Diabetes Interventions and Complications (DCCT/EDIC) Study Research Group. "Intensive diabetes treatment and cardiovascular disease in patients with type 1 diabetes." *N Engl J Med.* 2005 Dec 22;353(25):2643-53.

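### Chapter 6's 95%/80% power for Part 2 does not follow from its stated correlation of 0.69 and ignores the wear limit from Part 1; whether power is lost depends on that limit

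*Combined protocol and SAP*

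**What the plan says.** Chapter 6, Part 2, Primary Outcome takes time to failure of each set as the primary outcome. From earlier studies it gives the control set a mean of 5.1 days with a standard "deviation of 1.7 days and intra-subject correlation of 0.69". On the worthwhile benefit it says "the subjects who wear the treatment set should extend wear by at least 1 day to" a mean of 6.1 days. It then claims 95% "power to detect a difference of 1 day in the average length of wear in a two-sided test" at alpha 0.05 with 40 subjects, and asks for at least 25 subjects for 80%. It names no test, mentions no wear limit and does not say how a set still working at the end of the wear period is analysed.

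A limit exists elsewhere. The Part 2 synopsis in Chapter 1 states "The planned duration of wear and visit schedule will be determined by the" findings of Part 1. Chapter 2 (Study Enrollment and Duration) and Chapter 3, Part 2 (initiation visit; second infusion set placement) repeat this, and the second set goes in when that period is over. No number of days is given for Part 2. The Part 1 synopsis calls the pilot a source of data "upon which to base the length of wear for" Part 2. Chapter 6 gives the pilot's aim: to "determine the maximum length of Lantern infusion set wear when 80% are still" functional, accidental pull-outs excluded.

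**The concern.** There are two separate problems in one calculation. First, the printed correlation and the printed power cannot both be right for a paired comparison of means. A reader cannot tell which correlation the sponsor relies on, and therefore how much margin 40 or 25 subjects provide.

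Second, the power refers to a difference in full wear time, but Part 2 observes wear only up to the limit. A set still working at that point contributes the limit, not its failure time. The recorded difference is then smaller than the true one, by an amount that depends on the limit. The 1-day target cannot be read directly from the trial's result unless few sets reach the limit. Part 2 is described as supporting registration and a 510(k) submission, so how such sets are counted should be settled before data are seen.

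**Working it through.** **Inputs.** Control mean 5.1, SD 1.7, correlation r = 0.69, difference 1 day, two-sided alpha 0.05, n = 40 and 25 (all Chapter 6). Assumed here: a paired t-test, and SD 1.7 for Lantern too (the document gives an SD for the control set only).

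**1. The plan's own figure, no limit.** SD of the paired difference = 1.7 × √(2(1 − r)); power from the noncentral t with noncentrality √n / SD of difference.
- r = 0.69: SD = 1.7 × √0.62 = 1.339. Power 99.6% (n = 40) and 94.8% (n = 25). 17 subjects would give 80% and 26 would give 95%.
- r = 0.5: SD = 1.7. Power 95.2% and 80.6%. The smallest n reaching 95% is exactly 40 (39 gives 94.7%), and for 80% exactly 25 (24 gives 78.8%).

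So the stated pair comes from using 1.7 as the SD of the difference; 0.69 was not used. Other readings tried (r = 0, r = 0.31, SD 1.9, independent arms) do not reproduce both figures.

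**2. Where the 80% criterion puts the limit.** If Lantern wear is normal with mean 6.1 and SD 1.7, and these inputs are not themselves limited, the day with 80% still working is 6.1 − 0.8416 × 1.7 = 4.67. The share of control sets still working then is P(Z > (4.67 − 5.1)/1.7) = 60%.

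**3. Recorded gain.** Mean wear up to limit c is c − [(c − μ)Φ(a) + σφ(a)], with a = (c − μ)/σ. At c = 4.669:
- Control: 4.669 − 0.484 = 4.185.
- Lantern: 4.669 − 0.190 = 4.479.
- Recorded gain: 0.29 day for a true gain of 1 day.

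**4. Power with the limit.** Limited differences are skewed with many exact zeros, so power was simulated (at least 10,000 trials per setting; paired t-test on wear up to the limit; normal wear, true gain 1 day).

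| Limit | Recorded gain | r = 0.69: n = 40 / 25 | r = 0.5: n = 40 / 25 |
|---|---|---|---|
| none | 1.00 | 99.6% / 94.8% | 95.2% / 80.6% |
| 7 days | 0.79 | 99% / 91% | 92% / 75% |
| 6 days | 0.59 | 96% / 83% | 86% / 66% |
| 4.67 days | 0.29 | 79% / 55% | 64% / 42% |

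**5. Sensitivity at the 80% day (r = 0.69, n = 40 / 25).**
- Shape, same mean and SD: Weibull 78%/55%, gamma 95%/78%, lognormal 98%/87%.
- Pull-outs excluded from the criterion, at the 10-15% of failures given in Chapter 1 (Etiology): limit 4.74-4.85 days; 82-84%/58-60% for normal wear.
- Earlier wear data themselves limited to 7 days (assumption): 80% day 4.96-5.11, recorded gain 0.47-0.49, power from 94%/76% (normal) to 99%/89% (lognormal), a shortfall of 0-4 points.
- Log-rank test with a variance that respects pairing: 77%/53% for normal wear.

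**6. Sensitivity at 7 days, true gain 1 day.** If the Lantern SD grows in proportion to its mean (r = 0.69), power is about 91%/75%. The paired log-rank gives 94-96%/78-81% across shapes with equal SDs.

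**7. Limit and effect are linked under the criterion.** An 80% day of 6 days implies a Lantern mean of 6 + 0.8416 × 1.7 = 7.43, a recorded gain of 1.03 days and power of about 100%. The link is loose in practice: with 24 Part 1 sets and a true 6.1/1.7, the observed 80% day varies by chance over roughly 3.8 to 5.6 days (95% range).

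**The case against.** The strongest reply is that nothing is at risk. The correlation slip makes the stated power conservative. A pilot meant to find the wear duration cannot state it in advance, and the criterion is given even though the number is not. Under that criterion a long limit can arise only if Lantern sets last long, in which case the gain exceeds 1 day and power is ample. The low figures need Lantern to perform exactly as assumed, near-normal or Weibull wear, and earlier data that were not limited; the documents establish none of these.

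Most of this stands. A reader might infer that Part 2 is underpowered. The documents do not support that: they fix neither the limit nor the shape of the wear distribution, and step 5 includes settings with little or no loss. A reader might also take the 10-day wording in the Chapter 4 risk section as the Part 2 limit, or as a contradiction. It is general risk text not tied to Part 2, and Chapter 2 gives 10 days as the Part 1 maximum, so it settles nothing.

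The opposite reassurance does not stand either. If the limit is set some other way, a limit of 6 or 7 days is safe only for certain correlations, tests and Lantern SDs (steps 4 and 6). And the case the criterion leads to, with Lantern exactly as planned, is the case the trial claims to be powered for.

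**Conclusion.** The stated 95%/80% is inconsistent with the stated correlation of 0.69, which gives 99.6%/94.8% (paired t-test assumed). That is an error of consistency and, taken alone, understates power.

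The power statement also leaves out a wear limit that other sections impose. If the 80% criterion sets the limit and Lantern wear is 6.1 days with SD 1.7, the limit is about 4.7 days, the recorded gain about 0.3 day, and power about 79%/55% at correlation 0.69 or 64%/42% at 0.5 (normal wear). Across the four shapes at 0.69 it runs from 78%/55% to 98%/87%, and the shortfall is only 0-4 points if the earlier data were limited to 7 days. A longer limit reached through the criterion would generally go with a larger gain and little or no loss.

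The conclusion is therefore conditional: the power of 40 and 25 subjects on what Part 2 will observe is not established. It is not shown to be inadequate. The results rest on the assumed test, equal SDs except where stated, and the wear distribution.

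**What to change.** Amend Chapter 6 before Part 2 starts:

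1. Make the power, the minimum number of subjects and the correlation agree, and print the SD of the paired difference used. If 0.5 was a deliberate choice over 0.69, say so and why.
2. Name a paired primary analysis that accounts for sets still working at the limit, for example the within-subject difference in wear restricted to the limit.
3. Once Part 1 fixes the limit, restate the 1-day target on that observable scale and give the power of 40 and of 25 subjects there, with a Lantern assumption consistent with the Part 1 result.

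The wear limit itself remains the sponsor's choice. The cost is wording and one recalculation after Part 1; the amendment itself adds no subjects, visits or procedures. The downside is that the restated power may be less favourable than the figures now printed.

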474 labeling. While the G6 system is FDA approved for non-adjunctive use without
475 calibration, we will ask patients to confirm blood glucose with glucometer prior to
476 removing an infusion set. Subjects will be instructed to check blood ketones using a
477 blood ketone meter if there is unexplained hyperglycemia. Unexplained hyperglycemia
478 refers to high glucose levels outside of the usual times they may occur, such as in the
479 initial few hours following a meal. If the CGM stops functioning during the study, the
480 subjects will insert a new sensor which will be provided to them. If there is an
481 accidental removal of an infusion set the participant will have access to a replacement
482 which he or she will be taught to place.
483

484 *Determination of an infusion set failure:*

485 They will be instructed to replace the infusion set, in the following situations.

- 486 1. The presence of serum ketones >0.6 mmol/L with meter glucose >250 mg/dL, in
487 the absence of illness, vigorous fat burning exercise, starvation or alcohol.
- 488 2. Unexplained hyperglycemia, >250 mg/dL, outside anticipated periods of
489 carbohydrate consumption, illness, missed insulin doses and menstruation. This
490 hyperglycemia cannot be reduced with appropriate correction doses of insulin
491 (such as a decrease of at least 50 mg/dL in 1 hour following a correction dose).
- 492 3. Signs of infection at the infusion site including pain, erythema or induration >10
493 mm in diameter.
- 494 4. Pump occlusion alarm
- 495 5. Adhesive failure (only the adhesive on the infusion set will be used)

496
497 *Recording of infusion site information:* At home they will exam their infusion site each
498 day for signs of redness and/or induration. If they detect redness or induration they will
499 record them in mm and send a text to study staff. At the time an infusion set is removed
500 they will record redness and induration in millimeters, and call one of the investigators if
501 there is more than 10 millimeters of erythema or induration. They will be given a ruler
502 for making these measurements. Subjects will record the time and date that infusion
503 sets or sensors are removed, and document why they removed the set and take a
504 picture of the infusion site after the infusion set is removed if there is ≥ 3 mm of

505 induration or erythema. The picture and infusion site measurements will be sent via text

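### Proportions by cause of failure cannot separate an effect of the set from longer wear; Chapter 6 should add cause-specific time-to-failure comparisons

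*Combined protocol and SAP*

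**What the plan says.** Chapter 6, Part 2, Exploratory Outcomes opens its list with "BMI, cause of infusion set failure, measurements of" erythema and induration. One sentence covers the analysis of these outcomes: "We will summarize the other secondary measures using means, standard deviation", and then "medians, ranges, proportions and 95% confidence interval, as appropriate". No sentence ties a statistic to cause of failure, but proportions are the only listed one that fits it. The section gives no denominator and no method that allows for time at risk or competing causes.

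Chapter 1, Etiology of Infusion Set Failures, states the expected mechanism: "Lantern is designed to reduce failures due to kinking. Other less common causes for" and, continuing, "set failure would probably not be affected by the Lantern; these include 10-15% being" accidental pull-outs. It adds 6-12% for adhesive loss and then "adhesiveness, 5-13% removed for pain and 5-10% for erythema/induration concerning" for infection. Pain and erythema/induration are thus separate causes there.

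In Chapter 3, Part 2, the third removal criterion combines them: "Signs of infection at the infusion site including pain, erythema or induration >10" mm. The same chapter has subjects record the time of and reason for each removal. It also returns them to their usual set after a failure beyond 24 hours, so time on the study set differs between set types.

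**The concern.** The causes of failure compete. A set that escapes occlusion stays in place and must end some other way or reach the wear limit. If the Lantern works as Chapter 1 expects, a table of causes by set will tend to show more adhesive, pain and infection-sign endings for the Lantern although the daily risk of each is the same for both sets.

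The synopsis says that Part 2 is meant to support a 510(k) submission, and Chapter 4 warns that longer wear may itself raise the risk of local infection. Readers will therefore look at infection signs by set. Crude proportions cannot tell them whether a difference comes from the catheter or from the extra days. Tabulating by removal criterion would also put pain-only removals in the infection row, which breaks the comparison with the shares quoted in Chapter 1.

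**Working it through.** **The plan's own figures.** The documents give no figure for causes by set. The nearest is the sample size. A paired t-test (difference 1 day, two-sided 0.05) with 1.7 as the SD of the within-subject difference gives 95.2% power at 40 subjects and 80.6% at 25, matching the stated 95% and 80%. Chapter 6 nevertheless describes 1.7 as the SD of wear on the control set, and that meaning is used below.

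**Inputs.** From Chapter 6: control mean 5.1 days, SD 1.7, Lantern target mean 6.1, 40 subjects. From Chapter 1: pull-out 10-15%, adhesive 6-12%, pain 5-13%, erythema/induration 5-10%. From the synopsis and Chapter 6, Part 1: wear length is set where 80% of Lantern sets still function, pull-outs excluded.

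**Assumptions.** Only the occlusion hazard falls, by enough to reach 6.1 days. All failures not listed above are occlusion-type. Pull-outs are removed.

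**Step 1: direction.** The per-set proportion failing from cause j by limit T is the integral from 0 to T of h_j(t)·S(t). Lowering the occlusion hazard raises S(t) and leaves h_j(t) unchanged, so this proportion rises. Total failures, 1 − S(T), fall. The share of cause j among failures therefore rises as well, whatever the hazard shape.

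**Step 2: control share of other causes (adhesive, pain, erythema/induration).** Low: (6+5+5)/(100−10) = 16/90 = 17.8%. High: (12+13+10)/(100−15) = 35/85 = 41.2%. The high value is an upper sum, because about 30% of subjects with erythema/induration also reported pain.

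**Step 3: SD-matched Weibull.** SD/mean = 1.7/5.1 gives shape 3.30 and control scale 5.685.
- Total-hazard multiplier for a mean of 6.1: (5.1/6.1)^3.30 = 0.554. Lantern scale: 5.685 × 6.1/5.1 = 6.80.
- Lantern share of other causes: 0.178/0.554 = 32%; 0.412/0.554 = 74%.
- Implied occlusion hazard ratio: (0.554 − 0.178)/(1 − 0.178) = 0.46; (0.554 − 0.412)/(1 − 0.412) = 0.24. The hazard ratio for the other causes is 1.00 by construction.

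**Step 4: effect of the wear limit.** Under this model 80% of Lantern sets still function at 6.80 × (−ln 0.80)^(1/3.30) = 4.32 days. At 7 days 33% survive, and at 10 days 3%. Expected other-cause endings per 40 sets = 40 × share × (1 − S(T)):

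| Limit (days) | Control share | Control | Lantern | Excess |
|---|---|---|---|---|
| 4.32 | 17.8% | 2.36 | 2.57 | 0.21 |
| 4.32 | 41.2% | 5.46 | 5.95 | 0.49 |
| 7 | 17.8% | 6.1 | 8.6 | 2.4 |
| 7 | 41.2% | 14.2 | 19.9 | 5.6 |
| 10 | 17.8% | 7.1 | 12.5 | 5.4 |
| 10 | 41.2% | 16.4 | 28.9 | 12.5 |

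At 4.32 days total failures are 13.3 (control) and 8.0 (Lantern) per 40. The share among failures still moves from 2.36/13.3 = 18% to 2.57/8.0 = 32%, almost wholly because the denominator shrinks. The two denominators can tell quite different stories.

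**Step 5: constant hazards.** The share rises by 6.1/5.1 = 1.20 (17.8% to 21.3%; 41.2% to 49.3%). The per-set excess, 40 × share × [1.196(1 − e^(−T/6.1)) − (1 − e^(−T/5.1))], is 0.5-1.2 sets at 7 days and 0.7-1.7 at 10 days. Constant hazards imply an SD of 5.1 days against the stated 1.7, so this is a low-end case and not a fit.

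**Step 6: which summaries remove the artefact.** Cause-specific hazards do: the ratio is 1.00. Failures per set-day do so only if the other hazards are constant. In a variant with occlusion shape 2, other-cause shape 3, a 16% share and no limit, the crude rate drifts from 0.0314 to 0.0426 per set-day. Cumulative incidence does not remove it, because it is the per-set proportion drawn by day.

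**The case against.** The case for leaving the plan alone has several parts, and most of them limit the size of the point.

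- **The plan does not prescribe proportions for this outcome.** The list is generic and applied as appropriate. This stands: the link is an inference, though no other listed statistic fits, and adding cause-specific methods would not contradict the text.
- **A higher per-set proportion is a true absolute risk for a set worn longer.** This stands. It misleads only if read as an effect of the set on that cause.
- **The excess may be invisible.** This stands for the per-set count at a short limit. Infection signs alone would move less than the pooled causes used here. The share among failures can still shift visibly.
- **Pain is handled alike for both sets.** This stands: merging pain with infection signs does not by itself favour either set. Subjects record why they removed the set, so pain may already be separable; the case report form is not shown.

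A reader might infer that the trial will declare a false safety signal against the Lantern. The documents do not support that, since no between-set test of cause is planned. Nor is cause of failure the only evidence on mechanism or infection. Erythema and induration measurements, pump delivery, ketone and CGM data are listed outcomes too, and the sites are examined at the final visit.

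**Conclusion.** The point holds as a modest, inexpensive improvement to an exploratory outcome. If the Lantern lowers only occlusion-type failures, the expected proportion of endings from other causes rises on both denominators with no change in those risks.

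The direction needs only that premise, which is the protocol's own. The size rests on assumptions. With the SD-matched Weibull the share among failures goes from 18% to 32%, or from 41% to 74%. The per-set excess runs from under half a set per 40 at about 4.3 days to 5-12 sets at 10 days, and is under two sets with constant hazards up to 10 days. Part 1 sets the limit, so the documents do not settle where in this range Part 2 will fall. The primary analysis is unaffected; the risk is misreading a descriptive table.

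**What to change.** In Chapter 6, Part 2, Exploratory Outcomes:

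- Keep the proportions for cause of failure, and state both denominators: all sets and failed sets.
- Add cause-specific time-to-failure comparisons between sets that account for the within-subject pairing, for example a Cox model stratified by subject. Use three groups: occlusion-type (criteria 1, 2 and 4), infection signs (criterion 3) and adhesive (criterion 5). Censor each at failure from another cause, at pull-out or at the wear limit.
- Name time to occlusion-type failure as a supporting analysis. The all-cause primary outcome stays as it is.
- Show cumulative incidence by day of wear as the absolute-risk display only, and say that it rises in the same way as the proportions.
- Give pain-only removals their own reason code, so that they can be tabulated apart from erythema/induration as in Chapter 1. The removal criterion itself does not change.

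The cost is SAP wording, some programming and one case-report code; removal times and reasons are already collected. The downside is few events per cause and wide intervals, more so with stratification by subject, so these results should be reported as estimates with intervals.
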